### **C.3 Stage 2: RCT**

The main study is a randomized, placebo controlled, double-blind crossover design with two treatment phases, each of approximately 7 weeks duration separated by a 3-week washout phase. In each 7 week treatment phase subjects will start study drug and titrate up to the maximum tolerated or targeted dose (20 mg/kg/day). Each subject will have a screening visit, baseline visit within 3 weeks, a low dose visit (when on 5 mg/kg/day for 10-15 days), an assessment visit while on 20 mg/kg/day, a first end of 7 weeks treatment phase visit (subject reaches maximum tolerated or targeted dose), a start of second 7-week treatment phase visit, a low dose visit (when on 5 mg/kg/day for 10-15 days), an assessment visit when on 20 mg/kg/day, a second end of 7 weeks treatment phase visit, and a safety visit (10 visits total). At the start of second 7-week treatment phase, subjects are dispensed and instructed to take study drug for the next treatment phase. To maximize compliance the coordinator calls the subject to remind them the next day's clinical visit. Subjects will be called every 3rd day during dose escalation and every 10th day during the dose maintenance period (up to

25 mg/kg/day). During phone calls subjects are monitored for adverse events, as well as changes in medical history and concomitant medications. Subjects are also called 3 days after stopping the study drug to check for signs of withdrawal. Further, in case CBD alters the reliability of self - report, repeated measures will be taken of a set of tests three times: at baseline, low dose and high dose. During the 10 days that subjects are on a low dose the measurements will be taken on the 3rd and 9th day by phone and at the visit on the 10th to 15th day. During the 28 days on high dose the measurements will be taken on the 12th and 22nd day by phone and at the visit on the 28th +/- 4 days. The phone assessments include the primary outcome (assessment of tolerability) and symptoms of hepatotoxicity, SCOPA-sleep, Anxiety short form, Depression short form, Emotional and behavioral dyscontrol short form, and EQ-5D-5L. At low dose visit (end of 10 days on 5 mg/kg/day), each 20 mg/kg/day visit and each end of treatment phase assessment visits, urinary CBD and metabolites will be tested. To increase compliance with taking study drug, subjects will be asked to fill out a diary at home. The diary will be a record of the date and time subjects take study drug, adverse and beneficial events, and whether they talked to study staff on phone that day, and if so what they were told to do with the dose. Study drug is dispensed at the baseline visit and at the start of the second 7-week treatment phase visit so that subject has enough to take until they return for the low dose visit. At that visit they are given enough to last through 20 mg/kg/day. At the 20 mg/kg/day visit they are given enough for the time on 25/mg/kg/day. As in Stage 1, the purpose of the visit at 20 mg/kg/day is to limit the amount of study drug that is dispensed at any one time and facilitate compliance, safety and drug control. In the instance that a subject does not reach the 20 mg/kg/day dose, due to intolerance, then they will come in when and if they need more study drug to complete 10-15 days on their maximal tolerated dose. If they have enough to last through the 10-15 days then they return for the Final Assessment visit, and therefore have fewer total visits.

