The study drug is obtained from GW Pharmaceuticals and is called Epidiolex. How the dose is started and escalated and what target dose is chosen is based on human literature but primarily on recommendations from GW staff. Animal data supports the use of CBD dosing up to 24 mg/kg/day. In human literature CBD has been well tolerated up to 1500 mg/day (~21 mg/kg/day). Studies using Epidiolex are described in GW's Investigational Brochure (IB) Edition 8, Section 7.3.1. Epidiolex has been used in six Phase 2 studies (mostly related to pain). Presently a study of patients with psychosis are taking 1000 mg per day. Also GW has initiated a clinical program of Phase 1-3 studies to investigate its effect in severe forms of epilepsy, i.e., Davet's syndrome and Lenox Gastaut syndrome. Based on their experience, GW has recommended the dose escalation and target used in this study. As noted, the purpose of Stage 1 study, n=10, is to check for tolerability of this dose regimen in PD patients. If Stage 1 shows that the maximal dose tolerated is less than 20 mg/kg/day, then the maximal targeted dose for the RCT study will be reduced accordingly.

A recent publication, Lancet Neurol 2016; 15: 270-78, shows evidence for using this dose. The study reported on the safety (n=128) and efficacy (n=137) of the study drug we are using, but in a pediatric (aged 1-30; mean

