10) population with severe epilepsy. Subjects were evaluated after 12 weeks on study drug, mean dose of ~23 mg/kg/day. Adverse events were reported in 128 (79%) of the 162 patients within the safety group. Adverse events reported in more than 10% of patients were somnolence (25%), decreased appetite (19%), diarrhea (19%), fatigue (13%), and convulsion (11%). Somnolence and fatigue were not dose related, diarrhea and weight loss occurred more often in subjects taking >15 mg/kg/day. Of note, the concomitant use of clobazam (an anticonvulsant medication) was highly associated with somnolence, meaning somnolence was less in those not on clobazam (21%) compared to those taking it (51%). Most adverse events were moderate and transient. SAEs deemed related to the study drug occurred in 12% of subjects, including 9 who had status epilepticus. However, of note, the study showed a ~50% reduction in seizures on study drug, and status epilepticus is a common problem in the population studied. Five subjects (3%) stopped the study drug due to an adverse event. Please see the article regarding clinically significant changes in safety blood analyses. Hepatotoxicity (< 1%), hyperammonemia (<1%), and thrombocytopenia (<1%) occurred only in subjects also taking valproate.

The maximum tolerated doses, in mg/kg/day, of the 10 subjects will be averaged, and adjusted to the next highest 5 mg/kg/day. That dose will be used as the targeted dose for the RCT. For example if the average of the maximal tolerated doses in Stage 1 subjects is 17.4 mg/kg per day, the targeted dose in the RCT will be 20 mg/kg/day. Or if the average of the maximal tolerated doses in stage 1 subjects is 22.7 mg/kg per day, the targeted dose in the RCT will be 25 mg/kg/day.

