### Dose escalation strategy

Study product will be started at 5 mg/kg/day and increased every 3 days by 2.5 mg/kg/day to 10 mg/kg/day. Then increase the dosage every 5 days by 5 mg/kg/day until the subject reaches a maximum targeted dose (20 mg/kg/day) or experiences intolerable adverse effects, in which case the dose will be dropped to the last tolerated dose, for 10-15 days. Tolerability will be assessed on the third day of each dose between 5-10 mg/kg/day and the fifth day of each dose between 10-20 mg/kg/day and the subject is instructed whether or not to change the dose starting the next day. Once a subject has been on a specific dose for at least 3 days (5-10 mg/kg/day) or 5 days (10-20 mg/kg/day), that dose can be changed for less or more than 3 (5-10 mg/kg/day) or 5 days (10-20 mg/kg/day) and can be changed by a smaller increment (2.5-5 mg/kg/day) as needed for tolerability. The maximal tolerated dose is determined by the PI or co-Investigator that is an MD, based on their clinical expertise.

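### Stage 1 stops at 20 mg/kg/day and section C.3 names 20 as the Stage 2 target, but the Stage 2 call text, dispensing text and schedule use 25, a dose no Stage 1 subject takes

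*Combined protocol and SAP*

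**What the plan says.** **Stage 1 cap.** Subjects escalate "until the subject reaches a maximum targeted dose (20 mg/kg/day) or experiences intolerable adverse effects" (section C.2, Dose escalation strategy). The Stage 1 aim, the adverse-event dosing rules and the Stage 1 schedule of events all end at 20 as well.

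**Rule for the Stage 2 target.** Under section C.1 the maximum tolerated doses of the ten subjects "will be averaged, and adjusted to the next highest 5 mg/kg/day". One of its two worked examples is that if the average "in stage 1 subjects is 22.7 mg/kg per day, the targeted dose in the RCT will be 25 mg/kg/day". The Stage 2 dose escalation text and the notes to the Stage 2 schedule repeat that Stage 1 determines the target.

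**Stage 2 dose as printed.**
- Section C.3, opening: "subjects will start study drug and titrate up to the maximum tolerated or targeted dose (20 mg/kg/day".
- Section C.3, call frequency: the maintenance period runs up to 25 mg/kg/day.
- Section C.3, dispensing: "At the 20 mg/kg/day visit they are given enough for the time on 25/mg/kg/day".
- Section C.3, Visits 4 and 8: 20 mg/kg/day is a five-day step.
- Stage 2 schedule of events, dose row: 25 on days 22-49 and again on days 92-119.

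**Threshold for lowering the target.** Section C.1 sets it at 20 ("If Stage 1 shows that the maximal dose tolerated is less than 20 mg/kg/day"). Section E sets it at 25.

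**Time at the top dose.** The Stage 2 dose escalation text and note l of the schedule give 28 +/- 4 days. The resupply sentence in section C.3, for subjects who do not reach 20, gives 10-15 days.

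**The concern.** The main purpose of Stage 2 is to assess safety and tolerability at the dose that Stage 1 determines, so that dose has to be unambiguous. The protocol justifies having two stages by the lack of definitive dose data in adults with a neurodegenerative disease. A reader who applies the section C.1 rule arrives at 20 or less. Staff who dispense from section C.3 or dose from the schedule arrive at 25, which Stage 1 never tests. Two sites of instruction in one protocol therefore lead to different maximum doses for the same treatment phase.

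**Working it through.** **Inputs.** Stage 1 maximum 20 mg/kg/day (section C.2); ten Stage 1 subjects; target rule and examples (section C.1); Stage 2 titration of 10-15 days at 5 mg/kg/day, then 3-day steps of 5 mg/kg/day, then 28 +/- 4 days at the top dose (section C.3); dose and day rows of the Stage 2 schedule.

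**1. Reproduce the plan's examples.** Read the rule as target = 5 x ceil(mean / 5).
- Mean 17.4: 5 x ceil(3.48) = 20, as stated.
- Mean 22.7: 5 x ceil(4.54) = 25, as stated.

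The rounding is right.

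**2. Apply the rule to what Stage 1 can produce.** The planned Stage 1 steps are 5, 7.5, 10, 15 and 20.
- Largest possible mean: (10 x 20) / 10 = 20.0, giving 5 x ceil(4) = 20.
- Nine subjects at 20 and one at 15: (180 + 15) / 10 = 19.5, giving 20.
- A mean of 22.7 cannot occur, because no individual value exceeds 20.
- If the phrase is read strictly, as the next multiple above the mean, a mean of exactly 20.0 gives 25. This needs all ten subjects to tolerate 20, and the resulting dose is one that none of them took.

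**3. Compare the thresholds.** Stage 1 cannot show that 25 is tolerated. The section E condition (maximal tolerated dose below 25) is therefore always met, and section E would always require a dose below the one the schedule prints. The section C.1 threshold of 20 fits the Stage 1 cap.

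**4. Size of the discrepancy if the schedule is followed.**
- Dose ratio: 25 / 20 = 1.25.
- Days at 25: 22 to 49 is 28 days, and 92 to 119 is 28 days. One of these periods is placebo, so the cannabidiol excess lasts 28 days.
- Share of the cannabidiol period: 28 / 49 = 57%. Share of all treatment days: 28 / 98 = 29%.

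**5. What a target of 20 does to the calendar.**
- Nominal end of period 1: 10 + 3 + 3 + 28 = day 44.
- Range from the stated windows: 10 + 3 + 3 + 24 = day 40 to 15 + 3 + 3 + 32 = day 53.
- Printed day 49 follows from a 25 step: 10 + 3 + 3 + 5 + 28 = 49.
- Writing 20 in place of 25 and leaving the day row alone would give 20 on days 17-49. That is 33 days, outside 24-32.
- The schedule also disagrees with itself on length: its header gives 47 days per period, while its day row gives 49 (days 1-49 and 71-119). The visit text in section C.3 uses 47 and 115.

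**The case against.** The strongest defence is that 25 is a placeholder. The Stage 2 escalation text and the schedule notes say that Stage 1 sets the target, so anyone using the schedule is told the dose is not fixed. Each step has a tolerability check, stopping rules apply, and a monitoring board oversees the trial. All of this stands and lowers the practical risk. It does not resolve the conflict: the schedule does not mark 25 as provisional, the dispensing sentence is a concrete instruction, and the opening of section C.3 prints 20.

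It is also fair to say that the documents do not settle which figure is the mistaken one. Several places accommodate 25, and a strict reading of the rounding phrase can reach it. That is a reason to state the intended dose, not to leave both.

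Three stronger readings are tempting but not supported:
- *That 25 mg/kg/day has no evidence behind it.* Section C.1 cites a mainly pediatric epilepsy study with a mean dose of about 23 mg/kg/day, and section C.9 tabulates adverse reactions at a daily maximum of 25. The supportable statement is that 25 is untested in this trial's Stage 1 subjects.
- *That 25 breaches the 1,500 mg/day human figure in section C.1 while 20 does not.* This holds only for body weights above 1,500 / 25 = 60 kg and up to 1,500 / 20 = 75 kg. Outside that band the two doses fall on the same side of the figure.
- *That the printed visit days prove 25 was intended, or was left over from an earlier design.* The windows let a 20 target end period 1 on any day from 40 to 53, which includes 47 and 49. Either explanation is conjecture.

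**Conclusion.** The inconsistency is real and should be corrected before Stage 2 opens. With Stage 1 capped at 20, the protocol's rule gives a Stage 2 target of at most 20, except on a strict reading when all ten subjects tolerate 20. The call text, dispensing text and schedule nevertheless use 25. Followed literally, subjects receive 1.25 times the Stage 1 maximum for about 28 days of the cannabidiol period; if the rule is followed instead, the excess is zero. The 28-day figure assumes the printed schedule and a subject who tolerates every step.

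This is a conflicting dose figure in the operating text. A reader might infer that safeguards are missing or that the tremor analysis is compromised. Neither follows: the step-by-step checks are in place, and the sample size and analysis do not depend on the target dose. The 10-15 days at the maximal tolerated dose in the resupply sentence is a linked error against 28 +/- 4 days elsewhere.

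**What to change.** Amend before Stage 2 opens:

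1. **Section C.1, target rule.** State that the target is the mean Stage 1 maximum tolerated dose rounded up to a multiple of 5 mg/kg/day, never above the highest dose given in Stage 1, so that a mean of exactly 20 gives 20. Replace the 22.7 example with one that can occur, such as 13.5 giving 15.
2. **One dose term.** In section C.3 and the Stage 2 schedule, replace both the printed 20 target and the 25 maintenance dose with: target dose (set by Stage 1, at most 20). Change the section E threshold from 25 to 20.
3. **Schedule days.** Rebase the rows so that the target dose is held for 28 +/- 4 days, which for a target of 20 means a period of about 44 days. Use one day count in the visit descriptions, the schedule header and the day row.
4. **Visits 4 and 8 and dispensing.** Hold these visits on days 2-5 of the target dose. Dispense at Visits 3 and 7 only up to that visit, and at Visits 4 and 8 for the rest of the phase. Keep the as-needed resupply rule for subjects who do not reach the target, with 28 +/- 4 days in place of 10-15.

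If 25 is intended, either extend Stage 1 to 25 or state that Stage 2 relies on the outside exposure cited in sections C.1 and C.9, and use 25 consistently.

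The cost is one amendment to wording and schedule. Extending Stage 1, if chosen, would add one dose step for Stage 1 subjects who tolerate 20.

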#### Quality of Life

- Parkinson's Disease Questionnaire (PDQ-39): is a reliable, valid, responsive, acceptable and feasible as the tool for the assessment of quality of life in Parkinson's disease patients. There are

39 questions in the long form Parkinson’s Disease Questionnaire, with 8 discrete scales: mobility (10 items), activities of daily living (6 items), emotional well-being (6 items), stigma (4 items), social support (3 items), cognitions (4 items), communication (3 items), and bodily discomfort (3 items). Patients are asked to think about their health and general well-being and to consider how often in the last month they have experienced certain events. Patients are asked to indicate the frequency of each event by selecting one of 5 options (likert Scale): never/occasionally/sometimes/often/always or cannot do at all.

- EuroQoL-5 Dimension-5 level (EQ-5D-5L): consists of 2 pages-the EEQ-5D-5L descriptive system and the EQ Visual Analogue Scale (EQ VAS). The descriptive system comprises 5 dimensions: mobility, self care, usual activities, pain/discomfort, anxiety/depression. Each dimension has 5 levels: no problem, slight problems, moderate problems, severe problems, and extreme problems. This is a widely used well validated simple assessment that is comparable across disease populations.

4. By assessing and comparing the proportion of subjects that drop out of the study due to study drug intolerance in the two groups (treatment vs. placebo).

**Secondary Specific Aim:** To examine the effect of CBD on severity & duration of tremor in PD.

**Secondary Outcome Measure:** Tremor is measured by the change from baseline to 10th day of 5 mg/kg/day (week 2 and week 12) and the end of each treatment phase (week 7 and week 17) change in total of scores on items 3.17 and 3.18 in part III of the MDS-UPDRS in the ON state (when anti-PD medication is working). Item 3.17 is rest tremor amplitude. Extremity ratings range from 0: Normal, No tremor to 4: Severe, >10 cm in maximal amplitude. Lip/Jaw ratings are similar but smaller amplitudes. Item 3.18 is constancy of rest tremor: 0 (no tremor) to 4 (present >75% of the exam).

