## **C.2 Stage 1: Open Label Dose Escalation Tolerability Study**

The dose escalation tolerability study will be conducted in 10 subjects (we will be recruiting up to 20 subjects to end up with 10) as an open label study lasting 4 weeks followed by a 2-week safety follow up. Subjects are closely monitored as the dose is titrated. Subjects will have a screening visit, a baseline visit within the next 4 weeks, a final assessment visit when they have been on the maximal tolerated or the targeted study drug dose for 10-15 days, and a safety visit 2 weeks later. The subject is to be on the maximal tolerated or targeted dose for 10-15 days, and return for the final assessment visit on that dose on any of days 10-15. The reason for a range of 10-15 days instead of exactly 10 days is to allow for some flexibility in getting subjects in for the study visit. Subjects will be called on the 3rd day of each dose between 5-10 mg/kg/day and the fifth day of each dose between 10-20 mg/kg/day. During phone calls subjects are monitored for adverse events, especially excessive daytime sleepiness, symptoms of hepatotoxicity, as well as changes in medical history and concomitant medications. At the final assessment visit, urinary CBD and metabolites will be tested. Subjects are also called 3 days after stopping the study drug to check for signs of withdrawal.

To increase compliance with taking study drug, subjects will be asked to fill out a diary at home. The diary will be a record of the date and time subjects take study drug, adverse and beneficial events, and whether they talked to study staff on the phone that day, and if so what they were told to do with the dose. To make sure the diary is recorded correctly, subjects will be asked to mail, email or fax a copy or image of the diary they filled out within 3 days of increasing from 5 to 7.5 mg/kg/day. This is so that diary errors can be corrected early.

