#### Dose escalation strategy:

In each of the two 7-week periods, study product (CBD or placebo) will be started at 5 mg/kg/day and increased as tolerated to a maximum weight-adjusted target dose that is determined as a result of the Stage 1 study. The dose escalation strategy is the same as in Stage 1 for each treatment phase, except that subjects will take 5 mg/kg/day for 10 -15 days, and have a study visit before increasing further. The reason for a range of 10-15 days instead of exactly 10 days is to allow for some flexibility in getting subjects in for the study visit. Then the dose is escalated at 3-day intervals (with 5 mg/kg/day increased each interval) until the subject reaches the maximum target dose or experiences intolerable adverse effects, in which case the dose will be dropped to the last tolerated dose. Tolerability will be assessed on the third day of each dose and the subject is instructed whether or not to change the dose on the next day. The maximal tolerated dose is the dose at which 5 mg/kg/day higher was not tolerated on two trials. When subject achieves the maximal tolerated dose or the maximum targeted dose, they will maintain that dose for 28 +/-4 days.

Urine collection, storage and transfer for cannabis and metabolites test protocol is as described in Stage 1.

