Visit 5-End of first 7-week (47 days) and Visit 9-second 7-week (115 days) treatment phase assessment visits: Same procedures are conducted as at the previous low dose visit, except for study drug and home diary dispensation. In addition, complete physical exam, detailed neurological exam, blood draw, urinalysis, ECG, and full cognitive assessment battery are done. Subjects will take their study drug upon their arrival to the

clinic and record the taking time. Blood is drawn for cannabis testing and safety labs 3 hours after the dose. Subjects will be monitored and vital signs and orthostatic blood pressures will be checked at 1 and 3 hours after taking the study drug.

Visit 6-Start of second 7-week treatment phase: Study drug and home diary dispensation and instruction will be performed. Formal drug interaction assessment will be done. Subjects take the first dose of study drug. Subjects will be monitored and vital signs and orthostatic blood pressure will be taken at 1 hour after taking the study drug. Subjects are also told to take study drug and record the taking time upon their arrival to clinic on the next clinical visit day.

Visit 10-Safety follow up: Vital signs, orthostatic blood pressures, history & complete physical examination, concomitant medications collection, formal drug interaction assessment, MDS-UPDRS, H&Y rating, UDysRS, RPW, MoCA, RBDSQ, QUIP-RS, C-SSRS, NPI, SCOPA-sleep, Anxiety short form, Depression short form, Emotional and behavioral dyscontrol short form, Fatigue Severity Scale, Pain Intensity and Interference short form, IRLS, PDQ-39, EQ-5D-5L, adverse event check, urine pregnancy test and cannabis lab testing are done. Hematology, complete metabolic profile, urinalysis and EKG will be done if there was a clinically significant change at the high dose evaluation visit compared to baseline visit. The PI will evaluate the subject for signs of withdrawal.

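### Stage 2 text gives subjects who stop below 20 mg/kg/day the Stage 1 hold of 10-15 days instead of 28 ± 4 days, so their end-of-phase visit would come 13-18 days on dose before nominal day 28

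*Combined protocol and SAP*

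**What the plan says.** C.3 (Stage 2: RCT) ends its design description with two sentences on subjects who, because of intolerance, do not reach 20 mg/kg/day. The first says "they will come in when and if they need more study drug to complete 10-15 days on their maximal tolerated dose". The second says "If they have enough to last through the 10-15 days then they return for the Final Assessment visit", and adds that such subjects make fewer visits.

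Other Stage 2 text sets a different hold:

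- C.3, earlier in the same description, on the repeated self-report measures: "During the 28 days on high dose the measurements will be taken on the" 12th and 22nd day by phone, and at a visit on day 28 ± 4.
- C.3, Dose escalation strategy: "When subject achieves the maximal tolerated dose or the maximum targeted dose, they will maintain that dose for 28 +/-4 days". The same section defines the dose concerned: "The maximal tolerated dose is the dose at which 5 mg/kg/day higher was not tolerated on two trials".
- Stage 2 schedule, note l: the end-of-phase visit falls on day 28 ± 4 of the maximal tolerated or the target dose, whichever the subject reaches.
- Section A, Stage 2 secondary outcome: tremor is measured at day 10 of the low dose and at "the end of each treatment phase (week 7 and week 17) change in total of scores on items 3.17 and 3.18".
- C.3, Procedures at each visit: "Visit 5-End of first 7-week (47 days) and Visit 9-second 7-week (115 days) treatment phase assessment visits".

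The shorter hold and the visit name match Stage 1. C.2 describes "a final assessment visit when they have been on the maximal tolerated or the targeted study drug dose for 10-15 days".

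**The concern.** The two closing sentences of the C.3 description look like Stage 1 wording left in the Stage 2 text. They are the only Stage 2 sentences that name the group stopping below 20 mg/kg/day, and they deal with when such a subject returns and for which visit. Staff managing one of these subjects could reasonably follow them.

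The visit affected is the one that supplies the end-of-phase tremor score and the analysis at the highest tolerated dose (section F, Stage 2). If it is brought forward, the subject is assessed after a much shorter time on the final dose than the rest of the trial, and the day-22 phone measures are never taken. Those calls include the tolerability assessment, which is the primary outcome.

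In a crossover the shortening need not be the same in both phases. If intolerance is more common on CBD, which is an inference because the documents give no frequency for this population, a subject could have a short hold in the CBD phase and a full hold in the placebo phase. The time/order term planned for the longitudinal models does not represent that difference.

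**Working it through.** **1. Which hold do the plan's own day counts imply?**

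Inputs: a low-dose period of 10 days; 3-day titration steps (Dose escalation strategy); a 21-day washout; and, in Appendix B, 5 days at 20 mg/kg/day with 25 mg/kg/day as the top dose.

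- Visit text, phase 1: 10 + 3×3 + 28 = 47. Phase 2: 47 + 21 + 47 = 115. Both match the stated 47 and 115 days.
- Appendix B, phase 1: 10 + 3 + 3 + 5 + 28 = 49. Phase 2: 49 + 21 + 49 = 119. Both match the scheduled days 49 and 119.
- With a 10-15 day hold, phase 1 would be 29-34 days (visit text) or 31-36 days (Appendix B). Neither matches.

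The intended hold is therefore 28 days.

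**2. Shortfall in days on the final dose**

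| Reference day of hold | Calculation | Shortfall (days) |
|---|---|---|
| Nominal, 28 | 28 − 15 to 28 − 10 | 13-18 |
| Earliest permitted, 24 | 24 − 15 to 24 − 10 | 9-14 |
| Latest permitted, 32 | 32 − 15 to 32 − 10 | 17-22 |

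The day-22 call is lost in every such phase. The day-12 call is also lost if the visit is on day 10 or 11.

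**3. Study day of the early visit**

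This step needs a titration path. Let L be the low-dose period (10-15 days). Take two failed 3-day trials of the next dose, as the definition of the maximal tolerated dose requires, and assume a 3-day step back between them. The hold starts on day L+10, L+13 or L+16 for a maximal tolerated dose of 5, 10 or 15 mg/kg/day. The early visit is 9 to 14 days after that.

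| Maximal tolerated dose | Early visit, L = 10 | Early visit, L = 15 | 28-day rule, L = 10 |
|---|---|---|---|
| 5 | 29-34 | 34-39 | 47 |
| 10 | 32-37 | 37-42 | 50 |
| 15 | 35-40 | 40-45 | 53 |

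Week 7 is days 43-49. At 5 or 10 mg/kg/day the early visit always falls before it.

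**4. Gap from the same subject's phase at target**

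C.3 opens with a target of 20 mg/kg/day, but its later text and Appendix B run to 25, so both are shown. At target 20 the hold starts on day L+7, with nominal visit day 44 for L = 10. At target 25, using Appendix B, it starts on day L+12, with nominal visit day 49.

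| Maximal tolerated dose | Target 20: nominal | Target 20: all windows | Target 25: nominal | Target 25: all windows |
|---|---|---|---|---|
| 5 | 10-15 | 1 to 24 | 15-20 | 6 to 29 |
| 10 | 7-12 | −2 to 21 | 12-17 | 3 to 26 |
| 15 | 4-9 | −5 to 18 | 9-14 | 0 to 23 |

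Nominal means L = 10 in both phases and a day-28 visit at target; for dose 5 and target 20, that is 44 − 34 = 10 to 44 − 29 = 15. All windows lets L vary from 10 to 15 in each phase and the target visit from hold day 24 to 32; for the same case, 40 − 39 = 1 to 53 − 29 = 24. The calendar gap can vanish. The shortfall in step 2 cannot.

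**5. Is drug level the problem?**

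Section III gives an oral half-life of 2-5 days. I assume linear one-compartment kinetics, once-daily dosing, L = 10 and the path in step 3. The level relative to steady state at the hold dose, on hold days 10 and 15, is then:

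- half-life 5 days: 1.10 and 1.05 (dose 5), 1.03 and 1.02 (dose 10), 1.01 and 1.01 (dose 15);
- half-life 2 days: 1.00-1.02 throughout.

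The level has essentially settled by the early visit. What is lost is duration of treatment, not exposure level.

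**The case against.** The strongest reply is that the plan already resolves the matter. The Dose escalation strategy covers subjects stopped by adverse effects and applies 28 ± 4 days to the maximal tolerated dose. Note l repeats the rule, and the same C.3 description schedules a day-28 visit. The disputed sentences close a run of text on dispensing, and the visit they name does not exist in the Stage 2 visit list, so they are a weak source for scheduling. On this view it is a leftover phrase of minor weight and with no demonstrated consequence.

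Part of this stands. The intended rule is not in doubt, and the disputed sentences are not the only text governing these subjects; they are only the text that names the 20 mg/kg/day threshold. The calendar-day gaps rest on an assumed titration path and can vanish. The 13-18 days are measured from nominal day 28; against the earliest permitted day the breach is 9-14.

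It does not remove the conflict. The second sentence goes beyond dispensing and sends the subject to an assessment. No text marks 10-15 days as superseded or as a deliberate exception. Knowing which rule was meant does not stop staff from following the one written for the subject in front of them.

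Adverse-event rates are not part of this point: section F compares events by dose level and allows Poisson models for events over time.

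**Conclusion.** The concern holds. The closing sentences of the Stage 2 description in C.3 are wrong as written and should be corrected. For subjects who stop below 20 mg/kg/day they replace a hold of 24-32 days with one of 10-15 days. That is 13-18 days short of nominal day 28 (9-22 across the permitted window), and the day-22 measures are lost. This result needs no assumption beyond the two stated windows.

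That the text was carried over from Stage 1 is an inference, but a strong one, since both the duration and the visit name are those of Stage 1. Unequal time on dose between a subject's CBD and placebo phases depends on intolerance being more frequent on CBD, which the documents do not quantify. The number of subjects affected is unknown, so no bias and no loss of power is claimed.

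**What to change.** In the last two sentences of the C.3 design description:

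- replace 10-15 days with 28 ± 4 days in both places;
- replace the Final Assessment visit with the end-of-treatment-phase visit (Visit 5 or Visit 9).

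As a separate clerical correction, align the visit numbers in notes k and l and in the Appendix B footnote with the visit descriptions: low dose is Visits 3 and 7, end of phase is Visits 5 and 9.

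The cost is protocol wording plus some resupply. Assume the supply given at the low-dose visit is the scheduled 3 days at 10, 3 at 15 and 5 at 20 mg/kg/day: 30 + 45 + 100 = 175 mg/kg. On the titration path assumed above:

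- Maximal tolerated dose 5: 75 mg/kg used, 100 left, enough for 20 days. This covers 10-15 days but not 28, so the correction adds a resupply.
- Maximal tolerated dose 10: 150 used, 25 left. Resupply is needed under either rule.
- Maximal tolerated dose 15: 240 needed before the hold begins, already 65 short. Resupply is needed under either rule.

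If the target is 20 and the low-dose visit supply is meant to cover the hold as well, the added resupply may not arise.
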